phenotype. An equally critical issue involves identifying which patients would respond best to hormonal treatment. Previous studies have yielded conflicting results on whether OCs improve pain modulation.^{24,25} These studies did not address dysmenorrhea or the usage of continuous OCs, which typically ablate withdrawal bleeding and withdrawal bleed-induced uterine nerve activation. *We hypothesize eliminating a painful stimulus with cyclical OCs will improve descending inhibition and reduce COS. (see Diagram 1)*

To determine whether alterations in pain are due to changes in descending inhibition, spinal cord excitability, or peripheral sensitivity we will use established tests for quantitative sensory testing. Changes in descending inhibition will be tested with conditioned pain modulation (**CPM**).²⁶ CPM involves presenting a counter-stimulus (such as cold water) to one part of the body and then simultaneously measuring the differential sensory response to a noxious stimulus elsewhere. The degree of descending inhibition is quantified by comparing the degree of blunted response from a counter-stimulus compared to the unmatched paradigm. Changes in spinal cord excitability will be tested with temporal summation.²⁷ Temporal summation involves evaluating pain report after repetitive stimulation of pain pathway sufficient to induce increased excitability of dorsal horn neurons. Changes in peripheral sensitivity will be evaluated with mechanical pressure testing. We will perform these tests across multiple body sites to determine whether changes in pain mechanisms are regional or body-wide. Performing these tests will allow us to determine whether eliminating a painful stimulus with cyclical OCs improves descending inhibition, spinal excitability, or overall peripheral sensitivity, which will be done in the Phase 2 protocol. The addition of EEG and EMG recordings will also allow us to determine brain and spinal mechanisms that affect nociceptive modulation.

If OCs are shown to improve descending inhibition, our results will extend prior findings in animals that demonstrate descending inhibition is needed to maintain chronic pain states.¹⁰ In humans, descending inhibition is impaired by repetitive pain insults^{28,29} but normalizes with successful interventions.³⁰ Additionally, our results will establish a relationship between descending inhibition and COS allowing for the development of preventative strategies.³¹

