Conditioned Pain Modulation (CPM) : CPM testing involves repeating pressure pain threshold testing in the presence of a heterotopic stimulus (in this case cold water). The testing stimulus will be a mechanical pressure on the left medial knee fat pad. As in the first task, pressure will be applied (0.5 kg/cm²/s ramp) until the participant achieves pressure pain threshold. Baseline pressure pain thresholds of the testing stimulus on the left knee and left shoulder will be determined. After waiting approximately 2 minutes, the conditioning stimulus will be applied by instructing the subject to insert their right hand up to their wrist into a bucket of water maintained between 0-6° C. After 10 s of immersion, subjects will be asked to rate their level of hand pain on a NRS 0-10 scale. After 20s of immersion, the pressure pain threshold will be re-applied using a 0.5 kg/cm²/s ramp rate at the knee and the participant will be asked to rate their knee pain at the time they reached threshold (i.e. pressed the button) on a NRS 0-10 scale. After testing (~20s of immersion), subjects will immediately remove their hand and the pressure pain threshold will be determined at the shoulder. After waiting 5- and 10-minutes after water immersion, the testing stimuli will be re-applied. This paradigm combines a method for measuring CPM⁴⁶ and methods for accurately measuring participation of descending inhibition.⁴⁷ CPM will be measured by the standardized differences in pain threshold, EMG activity and autonomic responses before and after heterotopic stimulation. This strategy will provide the most reliable measurement of descending inhibition.^{47,48}

Temporal Summation (TS): Participants will be instrumented to undergo tests of spinal pain modulation. Temporal summation will be tested using an algometer on the right medial knee fat pad. We will repeatedly apply an amount of pressure (0.5 kg/cm²/s ramp rate; ITI = 5-15 seconds) equal to the average of the participant's two pressure pain thresholds assessed during the first task. After each press, the participant will be asked to rate their pain on an NRS 0-10 scale. The pressure will be applied ten times or until the participant rates their pain as a 6, whichever comes first.

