collected electronically using REDCap at home. If requested, paper versions can be provided instead and mailed in. For participants continuing to Phase 2, the year 1 annual medical history questionnaire will usually take place during their assessment #3 visit. All participants that complete phase 1 (Screen + Assessment #1), including phase 2 dropouts, will be asked to complete the annual follow-up questionnaire.

Group (Sample Size)	H (20)	D (20)	D+COS (95)	PBS (40)	P (50)	MSA
Bladder Pain at FU (VAS)	0	0	2.5	3.0	-	0.85
Pelvic Hyperalgesia (VAS)	0	0	3	3	-	0.84
Pelvic Hyperalgesia (Time)	0	0	2	2.5	-	0.83
Pelvic Pain Thresholds	0	.5	.5	2.3	-	0.81
Bodily Pain Thresholds	0	1.5	2	2	2.3	0.91
Conditioned Pain Modulation	0	1-2	1-2	4 _a	2-4 _b	0.94
Menstrual Pain History	0	3.7	5	6	-	0.81
Temporal Summation	0	0	.7	.8	-	-
Estradiol	0	1-3 _c	1-3 _c	1-3	-	0.84
Depression/Anxiety	0	.3	.4	2	2-4	0.82

Table X: Sample sizes and hypothesized results in Z-scores or range of Z-scores (relative to healthy) for subjects that are healthy (H), have dysmenorrhea (D), have cross organ sensitization (D+COS), PBS, or chronic pain (P). MSA indicates Kaiser's measure of sampling adequacy. Numbers in italics indicated minimum detectable hypothesized score with current sample size. Z-scores based on preliminary data, or others indicated by subscript (a: ⁹, b: ^{11,13}). Effects temporal summation in these populations are unknown, but effect sizes as large as 1.1 have been reported for fibromyalgia. Dashes (-) indicate unknown effect size.

C1.h Data Analysis/Sample Size Requirements: The primary outcomes under this hypothesis will be [1] bladder pain at FU, [2] pelvic hyperalgesia (VAS, time to return to baseline pain), reflecting peripheral dysfunction/sensitization, and [3] centrally mediated hyperalgesia (CPM, bodily pain thresholds).

Factor [1], Bladder pain at FU: Our preliminary data on healthy subjects and women with dysmenorrhea, in combination with other studies investigating migraine and PBS, suggests effect sizes between 1.4-5.6 (Cohen's d). As a control comparison, we expect that women with chronic pain will have levels of bladder and pelvic sensitivity comparable to healthy subjects. We will perform t-tests for each of these three pain variables using pairwise contrasts and appropriate Bonferroni corrections for six group comparisons.

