(Z1) We will establish prospectively whether usage of cyclic or continuous OCs affects bladder pain sensitivity (on bladder filling test), in women with D+COS compared to women not on OCs. We are adequately powered to detect improvements in bladder pain, assuming a 35% dropout rate (conservative estimate, well exceeding previously published rate of 18-24%^{51,59}) and accommodating a 1:5.2 ratio of non-OC to OC users. We will perform repeated measures ANOVA to determine if experimental bladder pain improves at 6 months compared to baseline in women with D+COS (all having washed out at enrollment). Follow-up results at 12 months will be used to confirm findings. The effect size (f=0.9) was estimated from our preliminary data above. Analyses will be adjusted with E2 and P4 levels as a covariate to determine if the effect of OCs on bladder pain is largely due to its effects on circulating hormones with standard methods⁶⁰.

(Z2) Similarly, we will establish whether among D+COS patients' pelvic hyperalgesia and descending modulation, the hypothesized mechanisms responsible for bladder pain sensitivity, are affected by OC usage. We will perform a repeated measures ANOVA to determine whether significant improvements occur in pelvic hyperalgesia (VAS pain report, and time to normalize), pelvic PPT threshold, bodily PPT thresholds, temporal summation, and CPM in OC treated vs. untreated subjects at 6 and 12 months. Cohen's d's for drugs that affect PPT⁶¹, temporal summation⁶² and CPM⁶³ range between 0.6-0.9.

(Z3) Similar to z1, we will determine if bladder pain sensitivity improves among PBS patients pre- and post-continuous OC exposure using repeated measures ANOVA (6 and 12 months). Although hormonal treatment has been shown to improve bladder pain in 13/15 patients with PBS²³, the exact effect size is not known. Prospectively OC usage has been shown to reduce episodes of urinary calculosis pain (d=0.8)⁶⁴. We are adequately powered to detect an effect size as low as dz=0.6.

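### Temporal summation stops at a rating of 6, and the plan does not say how a series cut short by its own outcome is scored

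*Combined protocol and SAP*

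**What the plan says.** The procedure is in C1.e, Assessment Visit #1, under Temporal Summation. Pressure on the right knee is "equal to the average of the participant's two pressure pain thresholds assessed during the first task", so each woman is tested at her own threshold. "After each press, the participant will be asked to rate their pain on an NRS 0-10 scale". The series then ends as follows: "The pressure will be applied ten times or until the participant rates their pain as a 6, whichever comes first".

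Section A gives the purpose, "Changes in spinal cord excitability will be tested with temporal summation", and a concept, "Temporal summation involves evaluating pain report after repetitive stimulation of pain pathway sufficient to induce increased excitability of dorsal horn neurons", but no formula. The CPM paragraph just before it in C1.e does say how CPM will be measured; the temporal summation paragraph has no counterpart.

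The measure is used in three places:
- Table X hypothesises Z-scores for H, D, D+COS and PBS: "Temporal Summation 0 0 .7 .8". Its footnote adds: "Effects temporal summation in these populations are unknown, but effect sizes as large as 1.1 have been reported for fibromyalgia".
- Z2 (C2.h) applies repeated measures ANOVA to a list that includes "pelvic PPT threshold, bodily PPT thresholds, temporal summation, and CPM in OC treated vs. untreated subjects at 6 and 12 months".
- Z4 compares it between continuous and cyclical users if the main Z4 result is significant.

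C1.h does not list it among the Phase 1 primary outcomes.

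**The concern.** Temporal summation is the rise in pain over repeated presses. With a stop at 6, the rise that can be seen depends on where a woman starts: about 5 points from a first rating of 1, about 2 from a first rating of 4, and none if the first press is rated 6. The data are truncated by the outcome itself.

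Repeated measures ANOVA needs one value per woman per visit. Because the plan fixes none, the analyst chooses after seeing the data. Two common choices are the last rating minus the first, and the tenth minus the first in women who complete ten presses. The first caps the rise in women who summate most; the second drops them.

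At stake is the reading of a null or reversed result as evidence about spinal mechanisms, when the stop may have contributed to it. In Z2 a true fall on OCs can be understated, because the baseline rise was capped.

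**Working it through.** **1. The plan's own figures.**
- Z2 in Table Z (dz = 0.6, α = 0.05, power 0.80, n = 24): a two-sided paired t-test has noncentrality 0.6 × √24 = 2.94 on 23 df, giving power 0.804. It reproduces.
- Table X, two-sample t-test, noncentrality d × √(n₁n₂/(n₁+n₂)). For 95 v 20, √(1900/115) = 4.06, and d = 0.695 gives 80% power (table: 0.7). For 40 v 20, √(800/60) = 3.65, and d = 0.780 gives 80% power (table: 0.8).

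The hypothesised effects thus sit almost exactly at the minimum detectable ones, leaving little room for attenuation.

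**2. Simulation at 20 v 95.** The documents give no rating distribution, so all inputs here are assumptions: first-press SD 1.5, rise 0.15 per press (SD 0.2), press noise SD 0.6, integer ratings 0–10, stop at the first rating of 6 or more. The D+COS slope is raised so that the uncut tenth-minus-first effect is 0.7, which gives full-series power of about 81%.

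| Mean first rating, H | D+COS start | Stopped before press 10, H / D+COS | Last-minus-first | Completers |
|---|---|---|---|---|
| 1 | same | 9% / 22% | d 0.69, power 79% | power 64% |
| 2 | same | 20% / 37% | power 72% | power 55% |
| 3 | same | 36% / 56% | d 0.55, power 61% | power 41% |
| 4 | same | – | d 0.44, power 43% | power 27% |
| 3 | 1 point higher | 36% / 74% | d 0.30, power 22% | – |

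**3. Other assumptions** (first-press SD 1.2, total rise 1–2 points with SD 1.5–2, noise SD 0.5–1, true difference set near 0.7 SD).
- Equal first ratings with means of 2–4: uncut d 0.64–0.69, last-minus-first 0.32–0.63, completers 0.44–0.58.
- D+COS starting 1–2 points higher: last-minus-first −0.59 to 0.57, completers −0.10 to 0.42.
- In all 36 scenarios both scores gave a smaller d than the uncut series.
- Mean first rating 0.5–1: only 2–9% are stopped and last-minus-first hardly changes (0.55 v 0.55; 0.60 v 0.59).

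**4. Direction when summation does not differ.** If one group starts 1–2 points higher, from a mean of 2–3, last-minus-first gives d of −0.07 to −0.44 and completers −0.16 to −0.41. If the rises are equal but rating noise differs (SD 1.5 v 0.3), last-minus-first gives a false +0.45.

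**5. The alternative.** A mixed model with random intercept and slope was fitted to every press given.
- Linear rise: it recovered the true slope difference (0.157 v 0.160 per press; 0.164 v 0.163 with the higher start), with higher-start power of about 64% against 22% for last-minus-first.
- Rise that levels off: a straight-line model overstated the difference, 0.244 v 0.137 (ratio 1.8) and 0.325 v 0.130 with the higher start (ratio 2.5). Type I error stayed at or below 5%.

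**The case against.** The strongest reply is that the plan adopts neither score, so the distortion belongs to analyses it never named. A per-woman slope, a maximum or the number of presses to reach 6 would also give one value per woman. That is true, but it does not remove the gap. A simple slope over observed presses is not safe by default either (d 0.29–0.95 across the 36 scenarios), so the choice matters and is open.

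Other points stand and limit the claim:
- A reader might infer that the most pain-sensitive women are lost. The documents do not support this: the press is set at each woman's own threshold, so those cut short are women with high first ratings or strong summation, not simply those with low thresholds.
- A reader might infer that any score is biased toward no difference. Step 4 shows that the sign is not fixed.
- A reader might take 20 v 95 as a specified Phase 1 test. The C1.h t-tests cover three variables that exclude temporal summation; the Table X sizes only illustrate the group comparison hypothesised there.
- In Z2 as worded (treated v untreated, 52 v 10), even an uncut d of 0.7 has about 51% power (noncentrality 0.7 × √(520/62) = 2.03). The stop is not the main limit there.
- It is not the plan's only window on spinal mechanisms; section A also cites EEG and EMG recordings.
- A mixed model is not automatically valid: its slope depends on the assumed shape of the rise.

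**Conclusion.** The point holds in a limited form. The stop truncates the series by its own outcome, no temporal summation score is defined, and last-minus-first and completer scores are distorted. When the hypothesised difference exists they usually understate it; when groups differ in first rating they can reverse it.

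The size depends on the share of women who reach 6, which the documents do not give. Under assumed mean first ratings of 2–4 with equal starts, power at 20 v 95 falls from about 81% to 43–72% for last-minus-first and 27–55% for completers. Near a mean of 1 the last-minus-first loss is negligible, although completers still fall to about 64%. The 22% figure needs both a mean of 3 and a one-point higher start in D+COS.

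It would go too far to conclude that a null temporal summation result is uninterpretable or that the trial's main conclusions are threatened. This is a secondary mechanistic measure. The change should be made because it is cheap and the choice would otherwise fall after the data are seen.

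**What to change.** Leave the stopping rule as it is. In Z2, and for the Phase 1 group comparison behind Table X, state that temporal summation will be analysed from every recorded press rating with a likelihood-based linear mixed model:
- random intercept and slope per woman;
- group-by-press terms in Phase 1 and arm-by-visit-by-press terms in Z2;
- press entered as categorical, or with a curvature term, so that the result does not rest on a straight-line rise.

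Stopping depends only on ratings already recorded, so likelihood inference can use the shortened series without the unseen presses, provided the model fits. Women stopped at the first press stay in through the intercept.

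Report the share stopped before press ten by group and visit, and give presses-to-6 as a sensitivity analysis.

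The cost is a sentence or two in C1.h and Z2, with no new procedure or data. The downsides are a model-based score that is less simple than a difference, some loss of precision from a flexible press effect, and an effect size that still depends on the assumed shape. In a brief check with press categorical and a rise that levels off, the overstatement shrank but did not vanish, because each woman's own rise was still modelled as a straight line. The effect size should be reported with that caution.

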Since endometriosis and fibroids are identifiable anatomical conditions but understanding of their mechanistic contribution to dysmenorrhea and bladder pain is limited, we will include confirmed endometriosis participants and fibroids participants mixed within our dysmenorrhea

cohort to determine which effects produced by the primary analysis are due to anatomical conditions.

Participants are divided into two arms. Arm #1 participants include women ages 18-45 with dysmenorrhea, women with painful bladder syndrome (PBS), and healthy controls. Arm #2 includes women ages 18-45 with chronic pain or special healthy controls.

Our hypotheses on mechanisms responsible for the transition of menstrual pain to bladder pain will be tested through the following phases:

Phase #1 (includes Arm #1 and Arm #2 participants): *To determine if dysmenorrhea with concomitant bladder pain sensitivity exhibits neurophysiological features consistent with established CPP.* Women with dysmenorrhea without COS and women with chronic pain conditions outside of the pelvic region will be used as controls. Quantitative sensory testing (QST) and a noninvasive bladder pain test we previously have validated will be used to determine whether impairments in descending inhibition and pelvic sensitivity are responsible for vulnerability to COS in women with dysmenorrhea (with and without COS) and/or CPP.

Phase #2 (includes a subset of Arm #1 participants only): *To differentiate the individual contributions of circulating sex hormones and repeated sensitizing events (painful menses) on descending and peripheral mechanisms of bladder pain.* The same QST/bladder pain measures studied in Phase #1 will be retested within the D+COS and PBS subjects following a one-year randomized trial of cyclical vs. continuous OCs vs. no treatment. We added a second option for those who are randomized to Phase 2 that did not want to commit to their randomized group. They will be asked to come in for an additional assessment visit a year later. Participating in the randomized group is preferable but this will allow us to still obtain the follow up data that is important with these participants even if they choose not to participate in their assigned group.

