Inclusion criteria: Cases: 1) **Dysmenorrhea** cases will have: a) average menstrual pain $\geq 5/10$ (0=no pain and 10=the worst imaginable pain) with menses or withdrawal uterine bleeding from cyclic OCs without painkillers, b) menstrual pain in the region between the umbilicus and the perineum, above the level of the inguinal ligament and c) indication the participant has attempted to resolve pain by medical means (including NSAIDs and/or OCs). Participants who endorse bladder symptoms on the phone screen will be preferentially recruited; those who do not endorse bladder symptoms may be determined ineligible. We found our previous questions to have limited predictive value. Notably because we only want to collect the minimum amount of information necessary to determine eligibility on the phone screen, we may not ask all bladder questions (depending on what future statistics show in regards to what bladder questions accurately predict COS). Participants will complete a daily diary to verify menstrual pain during the screening period.³³ To be eligible as a dysmenorrhea case, a participant must indicate menstrual pain $\geq 5/10$ on at least one day during menses in their daily diary. In the circumstance that a participant originally assigned to the dysmenorrhea group does not reach a pain of 5 on any days on the daily diary, this will be handled on a case-by-case basis particularly if they used a continuous around-the-clock, effective pain treatment regimen. They must have no concurrent chronic pain diagnoses that affect daily life or a history of more than 24 migraines per year. 2) **D+COS participants** will meet criteria for Dysmenorrhea cases, with >15 bladder pain on a 0-100 visual analogue scale (VAS) during either first sensation or first urge at assessment visit #1. Initially participants will be enrolled as dysmenorrhea participants and their final eligibility for D+COS will be determined after their assessment #1 visit. 3) Diagnosis of **PBS participants** will be confirmed by medical records indicating chronic (>3 months) pelvic pain (average intensity $\geq 3/10$), pressure, or discomfort related to the bladder accompanied by at least one other urinary symptom such as persistent urge to void or frequency.³⁴ PBS

participants will also have records review to confirm the exclusion of other conditions by clinical examination or cystoscopy if necessary. PBS participants can have other chronic pain conditions.

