Participants reporting average menstrual pain $\geq 5/10$ on the phone screen (dysmenorrhea participants) will undergo a rapid version of the bladder test. Participants will be asked to rate their bladder pain on a 0-100 VAS scale when they reach “first urge.” If a participant arrives to the visit already at first urge, we will have them rate their pain and if not ≥ 10 , we will wait 15 minutes past first urge and have them rate their pain again. This is because the participant may not have been focusing on the feeling of their bladder. Participants not already at first urge will be encouraged to drink water (at least 20 oz) during the screening visit until they reach first urge at which point a pain rating will be attained. After they reach first urge, they can go to the bathroom and leave their urine sample. Those with $\geq 10/100$ pain at either first sensation or first urge and/or those with a GUPI scores ≥ 8 will be preferentially recruited into this study. In other words, we may eliminate some participants without evidence for COS (using the rapid bladder test FU pain score and possible using GUPI scores) after the screen visit. However, for those that continue, final group assignment will be determined by their ratings during assessment visit #1.

C1.c Between visit home tasks: Training of arm #1 and arm #2 participants to fill out daily diaries and how to use ovulation kits to determine their menstrual phase prior to their next visit will be provided by experienced research staff (for ovulation kits, only for those patients where menstrual phase changes can be defined). The daily diary will be completed using REDCap and asks them to rate their menstrual, bladder, and bowel pain (using a numeric rating scale where 0-no pain, 10-worst pain imaginable), describe any bleeding, enter results of ovulation tests, and list dose, type and use of painkillers. For special healthy controls and chronic pain participants (arm #2), the daily diary includes one additional pain rating where participants can choose the relevant area of pain from a scroll down menu and rate their pain in that area from 0-10. To protect confidentiality subjects will not enter identifying information and only use their assigned

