For the subset of participants who were using hormonal contraception to manage chronic or menstrual pelvic pain, and whom express concern about pain management during phase 1, the study doctor will discuss pain control options and if necessary, and the participant desires, prescribe Tylenol #3, Tramadol 50mg, or Norco 5/325. We expect these conditions to apply to a small subset of participants (less than 10). The participant may alternatively see their regular physician to address this issue. All other participants will be asked to manage their pain in the same ways they normally manage pain (e.g., over-the-counter painkillers, heat pads, etc.). All participants will be asked to indicate in their daily diary if they took any painkillers each day and if so, what medication and how much.

C1.e Assessment visit: Arm #1 and Arm #2 participants with regular periods and/or who are not using hormonal contraception will be asked to contact us when they start their first period after the assessment visit. The assessment visit will be scheduled during the anticipated participant's luteal phase (17-25 days after the start of their period adjusted if they typically have unusually short or long cycles). They also will be given ovulation kits and asked to complete them starting day 10 of their cycle up until their scheduled assessment visit to give us additional data about their menstrual phase. Bladder pain is less likely to be confounded with menstrual or ovulation pain during the luteal phase.

Special healthy controls and chronic pain participants (Arm 2) who do not have regular menstrual periods and/or are on hormonal contraception will not be required to use ovulation kits and instead visits will be scheduled at a time we do not expect any bleeding and approximately 2-6 weeks (but up to four months) after their screen visit.

The time between the screen visit and assessment visit may vary based on participant's personal schedule and ability to confirm ovulation status and group eligibility (if applicable) but will not exceed four months or be less than two weeks.

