Bladder pain test: All participants will first undergo bladder pain testing described in our validation study². Subjects will be provided directions for the bladder study. The bladder study involves voiding and obtaining baseline measurements of bladder volume with a 3D ultrasound abdominal transducer (GE Voluson 750, Wauwatosa, WI). After hydration with 20 oz of water, subjects are instructed to report when they reach standard levels of bladder urgency: first sensation, first urge, and maximum tolerance and volumetric measurements of the bladder will be made. At each of these time points and every 15 minutes, 0-10 VAS measurements of pain and urgency are recorded. After scanning at maximum tolerance, subjects will urinate in a graded toilet hat to allow for measurement and saving a urinary specimen. Samples will be banked for analyses. If the participant gives permission in the consent form, urine samples will continue to be stored after the study is completed for possible future analyses by our lab on women's health conditions. If the participant does not give permission in the consent form for analyses beyond the current study, their sample will be destroyed upon study completion.

Questionnaires: The previous validated questionnaires from the screening visit will again be employed during the bladder testing. Participants will also complete a handedness questionnaire.

Pressure Pain Threshold Test:

Basic 8: Participants will undergo body and pelvic floor pressure pain threshold testing following the same validated protocols in our published studies^{43,44} using digital external and internal vaginal pressure algometers. The body algometer (for example models see www.paintest.com) is a commonly used hand-held device in pain research that measures the amount of pressure applied to a 1 cm² circular rubber tip. The vaginal algometer consists of 2.5 cm² circular force sensitive resistor, which fits over the pad of the examiner's index finger under an exam glove (Detailed documentation was provided in a separate earlier supplement to the IRB). Prior to evaluation, subjects will report their baseline pain on an NRS 0-10 scale and will be asked to identify any painful body sites.

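### Primary outcome [1] tests D+COS against D on the same visit-1 bladder pain reading that separates the two groups, so that contrast is near-certain to be significant and is not a test of the hypothesis

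*Combined protocol and SAP*

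**What the plan says.** **Grouping rule.** The Arm 1 inclusion criteria (C1.a) define D+COS as a dysmenorrhea case with ">15 bladder pain on a 0-100 visual analogue scale (VAS) during either first sensation or first urge at assessment visit #1". C1.b confirms that the screening rating does not settle this: "final group assignment will be determined by their ratings during assessment visit #1".

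**Comparator.** The Phase #1 description in section A says "Women with dysmenorrhea without COS and women with chronic pain conditions outside of the pelvic region will be used as controls". D is therefore what remains of the dysmenorrhea cases once D+COS has been removed.

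**Outcome.** C1.h states "The primary outcomes under this hypothesis will be [1] bladder pain at FU". The bladder test at assessment visit #1 is taken by all participants and supplies this reading. The only other Phase 1 first-urge rating is the rapid test at screening, which is given to dysmenorrhea participants alone, so it cannot be the outcome for all groups.

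**Analysis.** C1.h, Factor [1]: "We will perform t-tests for each of these three pain variables using pairwise contrasts and appropriate Bonferroni corrections for six group comparisons". The six are not listed. Factor [2] says that bladder pain will be shown to be higher in D+COS than in H, D and P.

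No section acknowledges that the group label and outcome [1] share a reading, and none exempts the contrast.

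**The concern.** A t-test between two groups is informative when the outcome could have gone either way given how the groups were formed. Here one group is capped at 15/100 on the outcome by definition, and the other contains every dysmenorrhea woman above the cap. A difference in means follows from the sorting even if the women form one homogeneous population.

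The result would sit among primary, multiplicity-corrected tests and look like confirmation that D+COS is distinct. The effect size produced by sorting alone overlaps the 1.4-5.6 that C1.h anticipates for bladder pain, so its magnitude would not give it away.

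**Working it through.** **The plan's own figures.** C1.h gives no sample size for D+COS versus D on bladder pain. Its one fully specified calculation is H versus P on CPM (d = 0.78, ratio 2.6, alpha 0.05, power 0.80). Two-sided, n(H) = (1 + 1/2.6) x (1.960 + 0.842)^2 / 0.78^2 = 17.9, so 18, and n(P) = 2.6 x 17.9 = 46.4, so 47. That is close to the stated 20 and 50, and two-sided tests are used below.

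**Inputs from the documents.** Cut: above 15/100 at first sensation or first urge. Table X sizes: H 20, D 20, D+COS 95, PBS 40, P 50. Level: 0.05/6 = 0.00833.

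**Inputs assumed.** The documents give no distribution for the ratings and no correlation between first sensation and first urge.

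**One case by hand, with no phenotype.** Let both ratings be independent and exponential with mean 10.
- P(first urge <= 15) = 1 - e^(-1.5) = 0.777. The share labelled D+COS is 1 - 0.777^2 = 0.396.
- Mean first-urge pain in D: 10 - 15 x 0.223/0.777 = 5.69.
- Mean in D+COS: (10 - 0.604 x 5.69)/0.396 = 16.56.
- The corresponding SDs are 4.10 and 12.46. Pooled SD = sqrt[(94 x 12.46^2 + 19 x 4.10^2)/113] = 11.49.
- Spurious d = (16.56 - 5.69)/11.49 = 0.95. Typical t = 0.95 x sqrt(95 x 20/115) = 3.8, against a critical value of 2.69.

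Simulation of this case rejects in 99% of runs, and it is among the mildest examined.

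**Across assumptions.** In 99 no-phenotype settings of 2,000 runs each, first-urge pain was exponential, clipped normal or zero-inflated; first sensation was 0.3, 0.6 or 1.0 times first urge; and the correlation was 0, 0.4 or 0.8.

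| Outcome [1] contrast | Rejection at 0.05/6 |
|---|---|
| D+COS vs D | 97.7-100% (Welch 99.95-100%); spurious d 0.94-3.54 |
| D+COS vs H | 3-100% |
| D+COS vs P | 8-100% |
| PBS vs D | 0.4-99.8% |
| PBS vs H, P vs H | 0.3-1.6% (nominal 0.83%) |

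Separate no-phenotype runs gave 0.5-96% for D vs H and 0.2-99.9% for P vs D. When first-urge pain was replaced by an independent draw that played no part in grouping, D+COS vs D rejected in 0.6-1.5% of runs. The cut itself produces the effect.

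**Where it breaks down.** The rule is either/or, so D+COS can include women at 15 or below at first urge. With independent exponential ratings and a first-sensation mean of 20, rejection falls to 57.5% (Welch 98.8%) for a first-urge mean of 10, and to 0.9% (Welch 16.6%) for a mean of 5. At correlation 0.5 these return to 99.5% and 70.2%.

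**Which six?** Three sets of six are compatible with C1.h: the contrasts it names for bladder pain (D+COS vs H, D and P; PBS vs H and D; P vs H); each of D+COS, PBS and P against D and H; and all pairs of H, D, D+COS and PBS. Every set contains D+COS vs D. Contrasts using D or D+COS number 4, 4 and 5 of the six respectively.

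**The case against.** **It is only a check of the phenotype, and the rule is stated openly.** The rule is indeed open, and a careful reader can see it. But C1.h lists the reading as a primary outcome with corrected t-tests, not as a check. Calling it a check is the change requested.

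**The simulations rest on invented distributions.** That is fair for the other contrasts. Ranges such as 3-100% show that they may be distorted and say nothing useful about how much. It matters less for D+COS vs D, where the result held across every setting in which first sensation hurts no more than first urge.

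**Group sizes may differ.** B.1 expects 515 women with dysmenorrhea to complete Phase 1, whereas Table X shows 20 D and 95 D+COS. A larger D group would make a spurious rejection more likely, not less.

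**The two VAS scales differ.** The visit-1 test says "At each of these time points and every 15 minutes, 0-10 VAS measurements of pain and urgency are recorded", while the cut is on 0-100. The passages must be reconciled, but the circularity does not depend on the scale.

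**The screening rating could serve instead.** It does not set the final split, but women with higher scores on it "will be preferentially recruited into this study", so it too is selected and is not a clean replacement.

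**Stronger readings.** A reader might infer that the contrast is significant whatever the data. The either/or rule does not support that: exceptions exist, though they are implausible because first sensation precedes first urge as the bladder fills. A reader might also infer that the Phase 1 primary analysis fails as a whole. The documents do not support that either: pelvic hyperalgesia, CPM and bodily thresholds play no part in the grouping rule, and the expected outcomes in C1.i rest on those and on menstrual pain.

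**Conclusion.** The concern holds for one named primary contrast. With no true phenotype and Table X sizes, D+COS vs D on visit-1 first-urge pain is significant at 0.05/6 in about 97-100% of runs, so its p-value does not test the hypothesis. This assumes that first sensation hurts no more than first urge; it fails only if first sensation hurts much more and is nearly unrelated.

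Every other outcome [1] contrast using D or D+COS is shifted by the same cut, by an amount that depends on distributions the documents do not give. This includes D vs H and P vs D if they are among the unlisted six. Contrasts among H, PBS and P alone keep their nominal error rate. Nothing here shows that the D+COS phenotype is absent; it shows that this test cannot establish it.

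**What to change.** 1. In C1.h, remove D+COS vs D on visit-1 first-urge pain from the inferential primary tests and report it descriptively as a check of the grouping rule.
2. List the remaining outcome [1] contrasts and keep 0.05/6. If five remain, 0.05/5 = 0.010 would be available, but keeping 0.00833 avoids loosening any threshold.
3. State that any outcome [1] contrast involving D or D+COS is affected by selection on the outcome, and interpret it accordingly.

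The cost is wording only: no new data, visits or sample size. The downside is that outcome [1] loses a near-guaranteed positive contrast.
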